3.2.4 Handling of Incomplete or Missing Data

Missing data will not be imputed in general and will be reported as missing in all listings. For categorical variables, patients with missing data are not included in calculations of percentages unless otherwise specified.

Missing start and end dates for AE and concomitant medication (CM)

The assumption will be the worst or most conservative judgment when imputing AE and CM start and end dates. The purpose of imputing a start date is to help define whether the AE/CM started while taking study drug.

For a partial or missing start date:

• If the day is missing, the first day of the month will be imputed. If the missing day is the same as the month of first dose of study drug, then the first dose date will be imputed.

- If the day and month are missing, the first day of January will be imputed. If the year is the same as the first dose date, then the first dose date will be imputed.
- If the date is completely missing, the first dose date will be imputed. If the end date suggests it could have started prior to this, the first day of January of the same year as the end date will be imputed.
- When imputing a start date, the start date will ensure that the new imputed date is sensible, i.e., is prior to the end date of the AE or CM.

For a partial or missing end date:

- If the day is missing, the last day of the month or the last assessment date, whichever is earlier, will be imputed.
- If the day and month are missing, the 31st of December or the last assessment date, whichever is earlier, will be imputed
- If the date is completely missing, there will be a need to look at whether the AE/CM is still ongoing before imputing a date. If the ongoing flag is missing, then it will be assumed that AE is still present, or CM is still being taken (i.e., do not impute a date). If the AE/CM has stopped, then the last assessment date will be imputed.

These data imputations are for categorization purpose only and will not be used in the listings.

If the assessment of the relationship of the AE to tesevatinib is missing, then it will be assumed that the AE is related to tesevatinib, and the AE considered as such in the frequency tables of possibly related AEs. No imputation should be done at the data level.

Missing event dates

Event date will be imputed only when day is missing, and the purpose of imputing an event date is to most conservatively calculate time to event.

If the day is missing, the first (mid, last) day of the month will be imputed for undesired (neutral, desired) event. If the missing day is the same as the month of first dose of study drug, then the first dose date will be imputed for undesired event.

These data imputations are for time to event calculation only and will not be used in the listings.

3.3 Analysis Populations

The following are the set of analysis populations.

Screened Population: All subjects who sign the Informed consent form (ICF) will be included in the Screened Population.

Safety Population: The Safety Population is defined as all subjects who receive at least 1 dose of study medication. Subjects will be analyzed according to the study drug they actually received.

Intent-to-treat (ITT) Population: The ITT population is defined as all randomized subjects. Subjects will be analyzed according to the study medication to which they were randomized.

Modified Intent-to-treat (mITT) Population: The mITT Population is defined as all subjects who receive at least 1 dose of study medication. The mITT Population will be used for tables of demography and baseline characteristics. Subjects will be analyzed according to the study medication to which they were randomized.

Efficacy Population: The Efficacy Population is defined as all subjects in the mITT population who complete at least 12 months of tesevatinib or placebo treatment and have a centrally read MRI at baseline and after 12 months of treatment. Subjects will be analyzed according to the study drug they actually received. This will be the primary population for efficacy analyses.

3.4 Subject Disposition and Evaluability

The analysis populations defined in Section 3.3 and the number of subjects discontinuing from the study and the primary reason for discontinuation will be summarized.

3.5 Protocol Deviations

All protocol deviations will be identified and classified as major or minor before clinical database lock and will be presented in a listing.

Major Deviation: Protocol deviation that may impact the accuracy, and/or reliability of the study data or that may impact subject rights, safety, or well-being.

Minor Deviation: Protocol deviation that does not impact the accuracy, and/or reliability of the study data or subject rights, safety, or well-being.

3.6 Demographics and Baseline Characteristics

3.6.1 Demographics

Descriptive summaries of demographic and baseline characteristics will be presented by treatment group and overall, for the mITT population. Demographics and baseline characteristics will be reviewed to assess the comparability of the treatment groups at baseline. Continuous variables such as subject age, weight and height will be summarized using number of observations, mean, standard deviation, median, minimum, and maximum values. Categorical variables such as subject sex and race will be summarized using number of observations and percentages for each category.

3.6.2 Medical History

Medical history will be summarized by primary System Organ Class (SOC) and Preferred Term (PT) for each treatment group. Medical history will be coded using Medical Dictionary for Regulatory Activities (MedDRA) Version 20.1 (or higher) terminology.

3.7 Prior and Concomitant Medications

Concomitant medications will be coded using the World Health Organization Drug Dictionary (MAR2017B2). Prior medications are defined as those medications that began and stopped before the start of study treatment. Concomitant medications are defined as medications taken after the start of study treatment and during the study period, including those began before but ongoing at the start of study treatment. If a medication start date is partially or fully missing and it is unclear as to whether the medication is prior or concomitant, it will be assumed that the medication is concomitant.

Number and percentage of incidence of prior and concomitant medications will be summarized according to Anatomical Therapeutic Class (ATC) and preferred drug name.

3.8 Treatment Exposure

Summary statistics for the duration of exposure to investigational product will be presented by treatment group. In addition, the number of dose interruptions will be provided in by-subject listings. The duration of exposure is defined as:

Duration of exposure (days) = (Date of last dose - Date of Study Day 1) + 1.

3.9 Efficacy Analyses

Listings for all efficacy data will be presented. Results will be presented by Treatment Group. The Efficacy Population will be the primary analysis population for efficacy analyses, with the mITT Population being used for sensitivity and supplemental analyses.

3.9.1 htTKV Logarithmic Transformation

To reduce heterogeneity, a logarithmic transformation (log₁₀) will be applied to the htTKV data prior to the analysis of covariance (ANCOVA) analyses (ie, defined in Sections 3.9.2) and mixed model repeated measures (MMRM) analyses (ie, defined in Section 3.10.1). The log10 transformation will apply to both the baseline and post-baseline htTKV assessments .

3.9.2 Primary Endpoint Analysis

The primary efficacy endpoint is the change from baseline in htTKV at Month 12. An ANCOVA model including treatment group as a factor and the baseline htTKV (log_{10} transformed) as a covariate will be used for efficacy analyses. The dependent variable is the log10 transformed change from baseline (ie, log_{10} (Month 12 htTKV) - log_{10} (Baseline htTKV)).

The 2-sided Type I error rate will be set at an alpha level of 0.05.

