3 STATISTICAL METHODS

3.1 General Methods

3.1.1 Computing Environment

All statistical programming and data analyses will be performed using SAS® Version 9.4 on a Windows platform.

3.1.2 Sample Size Justification and power calculations:

Based on the results presented in Caroli, et.al.¹ it is anticipated that the mean change from baseline in htTKV at 12 months will be 83.6 (\pm 90.0) mL in the placebo group. Assuming the mean change from baseline in htTKV at 12 months is 26.4 mL for the tesevatinib group, 40 subjects per group would yield approximately 80% power to detect a difference between treatment groups based on a 2-sided t-test with a Type I error rate of 0.05. Ten additional subjects per group will be added (i.e., for a total of 50 subjects per group) to adjust for dropouts and differences in analysis methodologies (e.g., the htTKV data will be log-transformed).

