3.9.3 Secondary Endpoint Analyses: Change from Baseline in eGFR

A secondary endpoint is the change from baseline in eGFR at months 12, 18, 24, and 30 days post-dose using the MDRD-4 formula (see Table 1).

For the 30 days post-dose endpoint, the change in eGFR from baseline to posttreatment follow-up is annualized (divided) by each subjects' treatment duration (in years). This normalization is necessary, otherwise the treatment group having more dropouts or earlier dropouts may bias the results.

At each timepoint (ie, months 12, 18, 24, and 30 days post-dose) and analysis of covariance (ANCOVA) model will be used to evaluate treatment effect. The ANCOVA model has eGFR as the dependent variable, treatment group as the factor, and baseline eGFR, patient age, and baseline htTKV as covariates.

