3.15 Mayo Classification Formula

Table 3 lists the Mayo Classifications (ie, 1A, 1B, 1C, 1D, and 1E) htTKV criteria for a given age as presented in Irazabel (2015)²; supplemental Table S2.

For classes 1A, 1B, 1C, and 1D the upper limits of htTKV are presented, for class 1E, the minimal value is presented (ie, as such the values in Table 3 for the 1D and 1E columns are equivalent).

For example, a 40 year old with an htTKV of 650 would have a classification of 1C.

Figure 1 provides an illustration of the Mayo Classification categories, as copied from "Figure 3" of Irazabel (2015)².

Age (years)	1A*	1B*	1C*	1D*	1E [†]
15	188	234	290	359	359
16	190	241	303	381	381
17	193	248	317	404	404
18	196	255	331	428	428
19	199	263	346	454	454
20	202	271	362	481	481
21	205	279	378	510	510
22	208	287	395	541	541
23	211	296	413	573	573
24	214	305	431	607	607
25	218	314	451	644	644
26	221	323	471	682	682
27	224	333	492	723	723
28	228	343	514	767	767
29	231	353	538	813	813
30	234	364	562	862	862
31	238	375	587	913	913
32	242	386	613	968	968
33	245	398	641	1026	1026
34	249	410	670	1088	1088
35	253	422	700	1153	1153
36	256	435	732	1222	1222
37	260	448	765	1295	1295

Table 3: Mayo Classification HtTKV Limits for Age

38	264	461	799	1373	1373
39	268	475	835	1456	1456
40	272	489	872	1543	1543
41	276	504	912	1635	1635
42	280	519	953	1734	1734
43	285	535	996	1838	1838
44	289	551	1040	1948	1948
45	293	567	1087	2065	2065
46	298	584	1136	2189	2189
47	302	602	1187	2320	2320
48	307	620	1241	2459	2459
49	311	638	1297	2607	2607
50	316	658	1355	2763	2763
51	321	677	1416	2929	2929
52	325	698	1480	3105	3105
53	330	719	1546	3291	3291
54	335	740	1616	3488	3488
55	340	762	1688	3698	3698
56	345	785	1764	3919	3919
57	350	809	1844	4155	4155
58	356	833	1927	4404	4404
59	361	858	2014	4668	4668
60	366	884	2104	4948	4948
61	372	910	2199	5245	5245
62	378	938	2298	5560	5560
63	383	966	2401	5893	5893
64	389	995	2509	6247	6247
65	395	1024	2622	6622	6622
66	401	1055	2740	7019	7019
67	407	1087	2863	7440	7440
68	413	1119	2992	7887	7887
69	419	1153	3127	8360	8360
70	425	1188	3268	8861	8861
71	432	1223	3415	9393	9393
72	438	1260	3568	9957	9957
73	445	1298	3729	10554	10554
74	451	1337	3897	11187	11187
75	458	1377	4072	11859	11859
76	465	1418	4255	12570	12570
77	472	1461	4447	13324	13324
78	479	1505	4647	14124	14124
79	486	1550	4856	14971	14971

[†]Minimal values shown for Class 1E

Figure 1: Illustration of Mayo Classification

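### Adding baseline age to the primary htTKV model would be an inexpensive, modest gain in precision; the age-free model is valid as it stands

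*SAP*

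**What the plan says.** **Primary endpoint.** SAP 3.9.2 analyzes the log10 change in htTKV at Month 12 with "An ANCOVA model including treatment group as a factor and the baseline htTKV", log10 transformed, as the only covariate. Protocol 9.10 and the synopsis list the same terms. SAP 3.10 reuses this model for Months 18, 24 and 30 days post-dose. The longitudinal htTKV model in 3.10.1 has no age term either, and no sensitivity analysis adds one.

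**eGFR.** The ANCOVA in SAP 3.9.3 carries "baseline eGFR, patient age, and baseline htTKV as covariates". No reason is given for using age there and not for htTKV.

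**Age and htTKV together.** SAP 3.15 says that "Table 3 lists the Mayo Classifications (ie, 1A, 1B, 1C, 1D, and 1E) htTKV criteria for a given age". SAP 3.11 uses the resulting class only to define subgroups.

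**Balance and analysis set.** Protocol 6.2 and 7.4 describe a randomization schedule generated by the vendor and name no stratification factor. The primary set (SAP 3.3) is subjects who completed 12 months of treatment and have central MRI readings at baseline and after 12 months.

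**The concern.** If expected growth over the next year depends on both kidney size and age, baseline htTKV alone leaves a predictable part of the outcome in the residual. Two subjects with the same htTKV, one aged 25 and one aged 58, get the same fitted value within an arm, although Table 3 puts them in different growth classes.

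Two things are at stake, both modest. One is precision, which a baseline variable recorded on every subject could improve without more patients. The other is protection against an age difference between arms. Nothing in the stated design balances age, and because the primary set is restricted to completers, a difference there could come from unequal dropout as well as from chance. If ages did differ, an age-adjusted result chosen after unblinding could be challenged; a pre-specified one could not.

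**Working it through.** **1. The plan's own figure.** Inputs from SAP 3.1.2: "the mean change from baseline in htTKV at 12 months will be 83.6" with SD "90.0) mL in the placebo group" (taken as common to both arms), 26.4 mL on tesevatinib, and a test "based on a 2-sided t-test with a Type I error rate of 0.05". The SAP's claim is that "40 subjects per group would yield approximately 80% power to detect a difference between treatment groups".

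- Difference: 83.6 − 26.4 = 57.2 mL. Standardized effect: d = 57.2/90 = 0.636.
- Power at 40 per group by the noncentral t distribution: 80.2% (81.1% by the normal approximation). The stated figure reproduces.

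**2. What Table 3 implies.** The limits were compared with 150 x (1+g)^age for g = 1.5%, 3%, 4.5% and 6%. All ages checked, between 15 and 79, match to the rounded mL:

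| Age | 1.5% | 3% | 4.5% | 6% |
|---|---|---|---|---|
| 35 | 253 | 422 | 700 | 1153 |
| 40 | 272 | 489 | 872 | 1543 |
| 60 | 366 | 884 | 2104 | 4948 |

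Inverting gives an implied yearly growth of (htTKV/150)^(1/age) − 1. For htTKV = 1000 mL:

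| Age | Implied growth per year | Class read from Table 3 |
|---|---|---|
| 25 | 7.9% | 1E (above 644) |
| 40 | 4.9% | 1D (872 to 1543) |
| 58 | 3.3% | 1C (833 to 1927) |

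All three subjects satisfy the htTKV inclusion criterion (floors of 500, 750 and 900 mL by age band).

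**3. How much age could explain.** The documents give neither the age and htTKV distributions nor an SD on the log scale, so these are assumptions. Eligible populations were simulated with age mean 38–42 and SD 8–10, pre-selection growth mean 4–5% and SD 1.5–2%, and the protocol's htTKV floors. For the growth implied by Table 3, R-squared was 0.30–0.50 with log10 htTKV alone and 0.96–0.97 with age added.

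Only part of this reaches the test, because most of the 12-month variation is other noise. On an assumed 1200 mL baseline, 90 mL is 7.5%. In one central scenario (implied growth SD 1.03 percentage points, R-squared rising from 0.376 to 0.963), the share of variance removed is approximately

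(0.963 − 0.376) x 1.03² / 7.5² = 0.587 x 1.061 / 56.25 = 0.011, or 1.1%.

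Across these scenarios the share was 0.9–1.7%, worth 0.3 to 0.7 points of power. Other assumed populations whose placebo growth is near the planned 83.6 mL give roughly 1–7%, with the higher values needing a wider age spread.

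**4. Conversion to power.** With a proportion r of residual variance removed, d becomes 0.636/√(1 − r). At 40 per group, with residual df 80 − 4 = 76:

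| r | Power |
|---|---|
| 0 | 80.1% |
| 1% | 80.5% |
| 2% | 80.9% |
| 5% | 82.1% |
| 7% | 82.9% |

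The gain is therefore about 0.4 points at 1% and 2.8 points at 7%.

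**5. Sensitivity to the SD.** If the total SD of 12-month change were 3% instead of 7.5%, the step 3 scenarios give 5–10% less residual variance and 2 to 4 points more power. The documents give no support for an SD that small.

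**The case against.** The strongest reply is that nothing is broken. Under randomization an ANCOVA without age keeps its type I error rate, the model is fully pre-specified, and it matches the protocol. That stands. A reader might infer that the primary test is biased, or that the SAP contradicts its own growth model; the documents support neither. Table 3 is a classification adopted from a cited source, the SAP writes no growth equation, and it never says that a subject's growth over the coming year follows the curve.

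The simulations are also partly circular: they generate growth from age and htTKV and then find that age predicts it. The gains are thus nearer a ceiling than an estimate. Larger gains need assumptions that clash with the plan. For example, ages uniform over 18–60 with mean htTKV near 1800 mL imply placebo growth of about 142 mL, against the planned 83.6 mL.

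Three further points have some force:

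- **Entry floors.** 500, 750 and 900 mL exceed the highest class 1B limit in each age band (422, 638 and 884 mL), so the slow-growth end is already excluded at the screening read. Step 3 applies these floors.
- **Mayo subgroups.** The subgroup ANCOVAs in SAP 3.11 use age and htTKV jointly. Splitting the sample by class does not, however, sharpen the overall comparison as a covariate would.
- **eGFR.** Age is a term in the MDRD-4 formula, so its place in that model has a reason specific to eGFR. The difference between the two models is not in itself an inconsistency.

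None of this removes the case for using a baseline variable recorded on every subject, at negligible cost, in a trial with no stated stratification factor and a completer-based primary set.

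**Conclusion.** The point holds as an optional improvement, not as an error. Table 3 gives a documented reason to expect age to predict htTKV change beyond baseline htTKV, and the primary model does not use it. At the planning assumptions the gain is small: from under 1 to about 3 points on 80% power, towards the upper end only with a wide age spread. It rests on assumed age and htTKV distributions and on the Table 3 relation holding for growth over the trial year. It would be larger only if the SD of log10 change were well below what 90 mL implies, and smaller to the extent that treatment slows growth in one arm, as the plan assumes (83.6 to 26.4 mL). Adjustment also guards against age imbalance, whether from chance or from unequal dropout before Month 12, though it cannot by itself remove the selection that a completer set brings. The documents' silence on stratification does not prove that none was used.

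**What to change.** Before unblinding:

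- Add continuous baseline age as a covariate to the SAP 3.9.2 model and to the Month 18, 24 and 30-day post-dose htTKV models in SAP 3.10.
- Amend protocol 9.10, and the matching synopsis text, so that protocol and SAP name the same primary model.
- Keep the model without age as a pre-specified sensitivity analysis.

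The cost is one degree of freedom (77 to 76 at 40 per group), a short change to the SAP and a matching protocol edit. It needs no new data and no more patients. If the sponsor prefers the present model, a sentence saying why age enters the eGFR analysis and not the htTKV analysis would help.

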3.9.3 Secondary Endpoint Analyses: Change from Baseline in eGFR

A secondary endpoint is the change from baseline in eGFR at months 12, 18, 24, and 30 days post-dose using the MDRD-4 formula (see Table 1).

For the 30 days post-dose endpoint, the change in eGFR from baseline to posttreatment follow-up is annualized (divided) by each subjects' treatment duration (in years). This normalization is necessary, otherwise the treatment group having more dropouts or earlier dropouts may bias the results.

At each timepoint (ie, months 12, 18, 24, and 30 days post-dose) and analysis of covariance (ANCOVA) model will be used to evaluate treatment effect. The ANCOVA model has eGFR as the dependent variable, treatment group as the factor, and baseline eGFR, patient age, and baseline htTKV as covariates.

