Study data will be summarized for disposition, demographic and baseline characteristics, efficacy, and safety parameters. Unless otherwise noted, study data will be summarized by treatment group. Categorical data will be summarized by frequency distributions (number and percentages of subjects) and continuous data will be summarized by descriptive statistics (mean, standard deviation, median, minimum, and maximum). All data will be presented in subject listings.

Efficacy analyses will be based on the Efficacy Population, defined as all randomized subjects who have completed 12 months of tesevatinib or placebo treatment and have a centrally read MRI at baseline and after 12 months of treatment. The primary efficacy endpoint will be the change from baseline in htTKV at Month 12. An analysis of covariance model including treatment group as a factor and the baseline htTKV as a covariate will be used for efficacy analyses. The Type I error rate will be set at an alpha level of 0.05. Additional efficacy endpoints include change from baseline in htTKV at Months 18 and 24.

Safety analyses will be based on the modified Intent-To-Treat Population, defined as all randomized subjects who received at least 1 dose of study drug. Treatment-emergent adverse events (AEs) will be summarized using Medical Dictionary for Regulatory Activities (Version 19.0 or higher) system organ class and preferred term and presented by treatment group. Safety endpoints will include AEs and clinical laboratory evaluations (including serum creatinine, cystatin C, and calculated eGFR).

Based on the results presented in Caroli, et.al.¹ it is anticipated that the mean change from baseline in htTKV at 12 months will be 83.6 (± 90.0) mL in the placebo group. Assuming the mean change from baseline in htTKV at 12 months is 26.4 mL for the tesevatinib group, 40 subjects per group would yield approximately 80% power to detect a difference between

treatment groups based on a 2-sided t-test with a Type I error rate of 0.05. Ten additional subjects per group will be added (ie, for a total of 50 subjects per group) to adjust for drop-outs and differences in analysis methodologies (eg, the htTKV data will be log-transformed).

STUDY SCHEDULE

Table 2: Schedule of Assessments

			Early Treatment Period			End of Study ^c
Assessments	Screening ^a (-28 Days)	Day 1	Day 14 (± 1 Day)	Day 28 (± 1 Day)	Every 28 Days ^b Beginning at Month 2 (± 1 or ±3 Days)	30 Days from Last Dose (± 3 Days)

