3.10 Supplementary and Sensitivity Analyses for Primary and Secondary Endpoints

The following are supplementary and sensitivity analyses for the primary and secondary endpoints:

- The primary and secondary efficacy endpoints will be performed on the mITT population.
- The htTKV at Months 18, 24, and 30 days post-dose will be analyzed in the manner as described in Section 3.9.2.
- A longitudinal analysis of htTKV (as described in Section 3.10.1)
- A longitudinal analysis of eGFR (as described in Section 3.10.23.10.1)

3.10.1 htTKV Longitudinal Analysis

An MMRM analysis will be performed on the htTKV data. The following is the MMRM model:

$$Y_{ij} = \beta_1 + \beta_2 \times Group_i + \beta_3 \times t_{ij} + \beta_4 \times t_{ij} \times Group_i + b_{1i} + b_{2i} \times t_{ij} + e_{ij}$$

Where:

Y_{ij}	is the $\log_{10}(hTKV)$ values for subject i at visit j (ie, at baseline; months 12, 18, and 24; and 30-days post-dose)
$Group_i$	is the treatment group indicator for Subject i (=0 if placebo, =1 if KD019)
t _{ij}	is the time (in years) from baseline of the htTKV assessment
β_{I}	is the intercept for the placebo group
β_2	is the intercept increment for the KD019 group (ie, $\beta_1 + \beta_2$ is the intercept for the KD019 group)
β_3	is the slope for the placebo group
eta_4	is the slope increment for the KD019 group (ie, $\beta_2 + \beta_4$ is the slope for the KD019 group)
b_{li}	Is the random intercept term for subject i
b_{2i}	Is the random slope term for subject i
e _{ij}	Is the error term for subject i , visit j .

Note: the random effects, b_{1i} and b_{2i} are assumed to be normally distributed with mean 0 and unknown variance covariance structure (ie, an unstructured 2×2 covariance matrix will be modelled). The error terms in the model, e_{ij} , are assumed mutually independent and normally distributed; and they are also assumed to be independent of the random effects, b_{1i} and b_{2i} .

This model will test for a difference in slopes between placebo and KD019 (ie, testing the fixed effect parameter β_4).

The following is the corresponding sample SAS Proc Mixed code for this MMRM model:

Table 2: Sample SAS Code of Longitudinal MMRM Analyses

```
** Sample SAS Code for MMRM **;
Proc Mixed Data=XXX;
Class Trt subject;
Model log_htTKV = treatment time treatment*time/s
Random intercept time / type=un subj=subject;
Run;
```

3.10.2 eGFR Longitudinal Analysis

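### Dividing the 30-days-post-dose eGFR change by own treatment duration lets a single very early stopper swamp the unweighted mITT re-run of that endpoint

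*SAP*

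**What the plan says.** SAP 3.9.3 defines the eGFR endpoint at Months 12, 18, 24 and 30 days post-dose. For the last of these only, "the change in eGFR from baseline to posttreatment follow-up is annualized (divided) by each subjects' treatment duration (in years". The stated reason is to prevent bias when one arm loses more subjects, or loses them sooner. Each timepoint is analysed by ANCOVA on treatment, baseline eGFR, age and baseline htTKV. No weights, floor or truncation are given. The dependent variable is called simply eGFR, although annualising serves no purpose unless the annualised change is meant.

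SAP 3.10 adds: "The primary and secondary efficacy endpoints will be performed on the mITT population". SAP 3.3 sets the entry condition: "The mITT Population is defined as all subjects who receive at least 1 dose of study medication". If treatment duration in 3.9.3 means the exposure of SAP 3.8, "Duration of exposure (days) = (Date of last dose - Date of Study Day 1) + 1", a one-dose subject has a divisor of one day. The Efficacy Population, by contrast, needs at least 12 months of treatment.

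SAP 3.10.2 also plans a random-intercept, random-slope model on the baseline and every later eGFR value. It does not name its analysis set. SAP 3.9 assigns mITT to sensitivity and supplemental work.

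**The concern.** The error in a difference of two eGFR values does not shrink because the subject took the drug briefly. Dividing by a small fraction of a year magnifies that error, and an unweighted ANCOVA then treats the result as equal to a rate measured over two years.

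Very short durations are foreseeable. Protocol 6.7 makes severe diarrhea in the first 28 days a reason for mandatory discontinuation. Protocol 4.3 asks sites to attempt end-of-study procedures for withdrawals, and SAP 2.4.2 schedules a creatinine 30 days after the last dose.

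This endpoint matters for two reasons:
- SAP 3.2.4 generally does not impute missing data, so subjects who leave before Month 12 add little to the mITT re-runs at Months 12, 18 and 24. The post-dose endpoint is where mITT brings them in.
- It is the only planned eGFR comparison made off drug. Protocol 1.2 reports creatinine rises of 10-14% on 50 mg without a rise in cystatin C.

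At stake is whether this re-run can tell the reader anything about dropout.

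**Working it through.** **1. The plan's own figure.** The only computed figure is the power for Month 12 htTKV: placebo "83.6 (± 90.0) mL in the placebo group", and "the mean change from baseline in htTKV at 12 months is 26.4 mL for the tesevatinib group". The difference is 83.6 - 26.4 = 57.2 mL, or 57.2/90.0 = 0.636 SD. With 40 per group the noncentrality is 0.636 × √(40/2) = 2.84, and the exact two-sided t-test at 0.05 has 80.2% power. The claim that "40 subjects per group would yield approximately 80% power" reproduces. It does not concern eGFR. What carries over is the planned loss in the Protocol synopsis: 50 randomised and 40 completing per arm, so 10 stoppers.

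**2. Multipliers (arithmetic only).** Multiplier = 365.25/days; noise variance relative to 24 months = (730/days)².

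| Last dose | Multiplier | Relative noise variance |
|---|---|---|
| Day 14 | 26.1 | 2,719 |
| Day 28 | 13.0 | 680 |
| Day 91 | 4.0 | 64 |
| Day 365 | 1.0 | 4 |
| Day 730 | 0.5 | 1 |

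Within the Efficacy Population the spread is at most about fourfold.

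**3. Variance model (assumed).** Var(annualised change) = s²/T² + b², with T in years. The documents give neither s nor b. I take s = 4, 6, 8 mL/min/1.73 m² and b = 2 per year. Letting the numerator run 30 days beyond T moves the SEs in step 5 by no more than about 0.02. At T = 2 the variance is 8, 13, 20. For 40 completers per arm, SE of the difference = √(2 × 8/40) = 0.63, and likewise 0.81 and 1.00.

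**4. One Day 28 stopper.** Take 40 completers, nine stoppers uniform over 4-11.5 months and one at Day 28. For stops uniform on (a, c) years, the mean of 1/T² is 1/(ac) = 1/(0.3333 × 0.9583) = 3.13. With s = 4:
- each of the nine has variance 16 × 3.13 + 4 = 54.1;
- the Day 28 subject has 16 × 13.04² + 4 = 2,727;
- the other 49 sum to 40 × 8 + 9 × 54.1 = 807;
- the share of the one subject is 2,727/3,534 = 77%.

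For s = 6 and 8 the share is 80% and 81%. At Day 14 it is 93-94%; at Day 58 it is 44-49%. So dominance fades at about two months.

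**5. Ten stoppers per arm.** SE = √{2[40·V(2 years) + 10·V(stoppers)]/50²}. For stops uniform over 0.5-11.5 months, 1/(ac) = 25.04, so with s = 4, V(stoppers) = 16 × 25.04 + 4 = 404.7 and SE = √(2 × 4,367/2,500) = 1.87.

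| Earliest stop | s = 4 | s = 6 | s = 8 | Ratio to completers |
|---|---|---|---|---|
| 0.5 months | 1.87 | 2.77 | 3.67 | 3.0-3.7 |
| 2 months | 1.04 | 1.50 | 1.97 | 1.7-2.0 |
| 4 months | 0.83 | 1.16 | 1.51 | 1.3-1.5 |

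**6. What weighting does.** With weights T² and stops over 0.5-11.5 months, the mean T² of a stopper is (0.9583³ - 0.0417³)/(3 × 0.9167) = 0.32. The 10 stoppers hold 3.2/(3.2 + 40 × 4) = 2.0% of the weight.

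**7. The random-slope model.** A small simulation (40 replicates, noise SD 6, slope SD 2.5, so approximate) gave these SDs of the estimated difference:
- one 28-day stopper per arm: 2.5 unweighted, 0.7 T²-weighted, 0.5 random slope;
- two 14-day stoppers per arm: 5.1, 0.8 and 0.5.

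**The case against.** Four points stand.

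First, a reader might infer that the plan has no working dropout check for eGFR. That is not so. The SAP 3.10.2 model does not divide by duration, can take in early stoppers' values, and is barely disturbed by them in step 7. Its limit is that it mixes on-drug and off-drug values, so the early creatinine rise can enter the slope; it is not a purely post-washout comparison.

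Second, a reader might infer that early stoppers will dominate. The documents give no distribution of stopping times. Dominance needs a stop within about two months and an obtained post-dose creatinine, and Protocol 4.3 promises effort, not a value. The one-dose case (multiplier 365) is an extreme.

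Third, the harm shown is imprecision. In a simulation under the step 5 assumptions (3,000 runs per setting, stops from 0.5 months) the unweighted Type I error was 3-4%, so inflated false positives are not supported.

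Fourth, weighting does not rescue the re-run as a dropout check: with about 2% of the weight on stoppers it nearly repeats the completer analysis. Weights built from duration, a post-randomisation quantity that treatment may affect, also need justification.

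**Conclusion.** The point holds as a conditional one. As written, the mITT re-run of the 30-days-post-dose eGFR change is a poor check on dropout whenever even one subject per arm stops very early and returns for a creatinine: adding the stoppers can make the estimate about three times less precise than leaving them out. The multipliers follow from the SAP; the SE ratios rest on the assumed noise, slope SD and stopping pattern, and timing of stops drives them most.

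The scope is narrow: one of four eGFR timepoints, in the sensitivity set, for a secondary endpoint that SAP 3.12 leaves without multiplicity control. It is still worth correcting before unblinding, because a rule introduced to protect against dropout makes the result hypersensitive to it, and later handling of an extreme value would be post hoc.

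**What to change.** In SAP 3.9.3 and 3.10:
- Keep the annualised ANCOVA for the Efficacy Population, and state that its dependent variable at 30 days post-dose is the annualised change.
- State that the SAP 3.10.2 model is fitted in the mITT set and is the dropout check for eGFR.
- If the annualised change is still run in mITT, weight it by duration squared (or by inverse variance), and do not interpret an unweighted version.

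The cost is a few sentences and a weight statement; no new data are needed. Two limits should be written beside the results: the weighted run is close to the completer analysis and is not itself evidence against dropout bias, and the 3.10.2 model does not isolate the off-drug comparison.
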